### **Prior/Concomitant Therapy**

18. Use of calcineurin inhibitors (e.g., tacrolimus, cyclosporine), vedolizumab, anti-TNF $\alpha$  therapeutic or any other immune system–targeted biological therapy within 12 weeks or 5 half-lives, whichever is longer, prior to screening.
19. Rectal therapy with 5-ASA or corticosteroids within 2 weeks of screening.
20. Use of any investigational drug within 12 weeks of screening.
21. Leukocyte apheresis within 12 weeks of screening.
22. Live vaccine(s) within one month prior to screening, or plans to receive live vaccines during the study or within 28 days of the last dose.

## **Prior/Concurrent Clinical Study Experience**

23. Donation of blood or blood products in excess of 500 mL within 3 months.
24. Exposure to more than 4 investigational treatments within 12 months prior to Day 1.
25. Current enrollment or past participation within the last 90 days immediately preceding signing of informed consent in this or any other clinical study involving an investigational study treatment or any other type of interventional medical research.

## **Diagnostic Assessments**

26. Abnormal hematologic values:
  - Anemia (Hgb < 9 g/dL)
  - Leukocytosis (WBC  $\geq 2 \times$  ULN)
  - Thrombocytopenia (platelet count < 100,000/ $\mu$ L)
  - Thrombocytosis (platelet count  $\geq 2 \times$  ULN)
  - Eosinophilia (eosinophil count  $\geq 2 \times$  ULN)
27. Abnormal hepatic enzyme or hepatic function values:
  - Alanine aminotransferase (ALT), aspartate aminotransferase (AST), alkaline phosphatase, or gamma-glutamyl transferase (GGT)  $\geq 2 \times$  ULN
  - Total bilirubin  $\geq 2 \times$  ULN
  - International normalized ratio (INR)  $\geq 1.2$
  - Albumin < 3 g/dL
28. Positive HIV antibody test.
29. Presence of hepatitis B surface antigen (HBsAg) or positive for total hepatitis B core antibody (HBcAb), or positive hepatitis C by PCR test result at screening or within the 3 months prior to starting study treatment.

## **Other Exclusions**

30. History of regular alcohol consumption within 2 months of screening defined as:

An average weekly intake of  $> 14$  drinks for males or  $> 7$  drinks for females. One drink is equivalent to 12g of alcohol: 12 ounces (360 mL) of beer, 5 ounces (150 mL) of wine or 1.5 ounces (45 mL) of 80 proof distilled spirits.
31. Any suspicion or history of alcohol abuse and/or suspicion of regular consumption of drug of abuse.

32. Patients under judicial supervision, guardianship or curatorship.

### **5.3 LIFESTYLE CONSIDERATIONS**

#### **5.3.1 Meals and Dietary Restrictions**

During the period from screening to the follow-up visit when participants are not resident in the unit, participants will be advised about the following requirements:

- Coffee or tea consumption should be no more than 3 cups/day, and methylxanthine containing drinks must be < 1 L/day.
- Alcohol consumption should be no more than 2 drinks/day.

One drink is equivalent to 12g of alcohol: 12 ounces (360 mL) of beer, 5 ounces (150 mL) of wine or 1.5 ounces (45 mL) of 80 proof distilled spirits.

#### **5.3.2 Caffeine, Alcohol, and Tobacco**

Caffeine and tobacco should be avoided during the residential period.

Consumption of alcohol will not be allowed from 48 hours before dosing until the end of the residential period.

#### **5.3.3 Activity**

Light ambulatory activities will be permitted, with the level of activities kept as similar as possible on all days in the clinical research unit during the study. *Participants are required to refrain from intense physical activity from 96 hours before screening visit until the final follow-up visit.*

### **5.4 SCREEN FAILURES**

Screen failures are defined as participants who consent to participate in the clinical study but are not subsequently randomized to study treatment/entered in the study.

The Investigator will maintain a screening log to record details of all participants screened and to confirm eligibility or record reasons for screening failure.

Individuals who do not meet the criteria for participation in this study (screen failure) may be re-screened. Re-screened participants should be assigned the same participant number as for the initial screening.

For re-screened participants, the following specific criteria must be met:

- Screening colonoscopy or flexible sigmoidoscopy for inclusion must be completed within 3 weeks prior to first dose.
- Serologies for hepatitis B, HIV, and PCR for HCV need not be repeated, and screening for latent tuberculosis infection need not be repeated if already done.
- Women of child bearing potential must repeat pregnancy testing.

- Screening laboratory evaluation beyond those itemized above must be completed within 35 days of the starting dose.
- For participants who were initially excluded due to active *Clostridium difficile*-related infection, participants must have completed therapy and have been stable off therapy for at least 7 days prior to repeat *Clostridium difficile* testing for Test of Cure (TOC). Those who test negative may be eligible for re-enrollment.

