Concomitant therapy with immunomodulators such as azathioprine/6-mercaptopurine (6-MP)/methotrexate may decrease the risk of ADA and neutralizing IL-2 antibody formation. Patients who are already on one of these therapies will continue; patients who are not already on these therapies will not be proactively started on them. The mechanism of action of RO7049665 is to induce tolerance via increases in  $T_{reg}$  activity. This tolerance induction can potentially mitigate the risk of ADA and neutralizing IL-2 antibody formation.

- **Increased Regulatory T Cells Causing Immunosuppression**

There is a theoretical risk of immunosuppression from increased  $T_{reg}$  cell count and an increased proportion of  $T_{regs}$  compared with total T cells. Infections, especially opportunistic infections, and malignancies are theoretical risks. Signs and symptoms of immunosuppression will be monitored and treated according to standard of care. A stopping criterion specific for  $T_{regs}$  increases has also been included.

- Injection Site Reactions

Localized injection site reactions (including erythema, pruritus and swelling) of mild intensity and resolving without treatment were observed following dosing with RO7049665 in the WP39826 study. There was a higher incidence at higher doses and injection site erythema was the most frequently observed event. The erythema was first observed at 2 to 6 days after dosing and had a duration varying from 3 to 54 days until complete resolution. Assessments of local skin reactivity and pain following injection will be performed in this study to further characterize injection site reactions. Administration of serial doses in the same *participant* should be done in different quadrants of the abdomen.

- Non-clinical Finding of Heart Rate Increase

Heart rate increases were observed in the 13-week good laboratory practice (GLP) study in cynomolgus monkeys. The heart rate increases showed complete reversibility in recovery. The effects seen on heart rate were likely linked to the acute phase response and/or elevated cytokine levels, both of which were more pronounced after Week 1 and thus are considered secondary to the pharmacologic action of the study drug. These effects were completely reversible. No trend towards increased heart rate was observed in the WP39826 clinical study after single dosing. Vital signs and ECGs will be monitored in this study. Further details are provided in the [RO7049665 Investigator's Brochure](#).

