### **Medical Conditions**

1. Diagnosis of Crohn's disease or indeterminate colitis.
2. History of infection with hepatitis B, human immunodeficiency virus (HIV), active hepatitis C virus (HCV) infection, or other chronic infection.
3. Active infections requiring systemic therapy with antibiotic, antiviral or antifungal or febrile illness within 7 days before Day -1.
4. History of primary or acquired immunodeficiency.
5. History of chronic pulmonary disease with resultant abnormal pulmonary function.
6. History of clinically significant cardiac or cardiovascular disease or uncontrolled hypertension.
7. Evidence of infection with *Clostridium difficile* or other intestinal pathogen within 35 days from the start of screening.
8. Evidence of colonic dysplasia that cannot be completely removed.
9. Females: Pregnant or lactating.
10. History of and/or current suicidal ideations

11. Any condition or disease detected during the medical interview/physical examination that would render the patient unsuitable for the study, place the patient at undue risk or interfere with the ability of the patient to complete the study in the opinion of the investigator, including malignant disease.
12. Symptomatic herpes zoster within 3 months prior to screening.
13. History of tuberculosis or a positive Quantiferon® Gold test.
14. History of clinically significant severe drug allergies, multiple drug allergies, allergy to any constituent of the product, or intolerance to topical corticosteroids.
15. Lymphoma, leukemia, or any malignancy within the past 10 years, except for basal cell or squamous epithelial carcinomas of the skin that have been resected with no evidence of metastatic disease for 3 years and in situ carcinoma of the cervix that was completely removed surgically.
16. History or presence of clinically significant ECG abnormalities before study drug administration (e.g., PQ/PR interval  $\geq$  220 ms, QT corrected for heart rate using Fridericia's correction factor (QTcF), <350 or  $\geq$  450 ms) or clinically significant cardiovascular disease (e.g., cardiac insufficiency, coronary artery disease, cardiomyopathy, congestive heart failure, family history of congenital long QT interval syndrome, family history of sudden death).
17. Fecal Microbiota Transplant (FMT), defined as receipt of any product derived from the feces of another human and administered per oral, per nasogastric or nasoduodenal, or per rectum within the last 6 months.

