## **8.10          TIMING OF STUDY ASSESSMENTS**

### **8.10.1       Screening and Pre-treatment Assessments**

Written informed consent for participation in the study must be obtained before performing any study-specific screening tests or evaluations. Informed consent may be obtained up to 3 months prior to randomization. Screening start will be defined as the first assessment done after signature of the informed consent form. Informed Consent Forms (ICFs) for enrolled participant and for participants who are not subsequently enrolled will be maintained at the study site.

All screening and pre-treatment assessments must be completed and reviewed to confirm that participants meet all eligibility criteria. The Investigator will maintain a screening log to record details of all participants screened and to confirm eligibility or record reasons for screening failure.

An Eligibility Screening Form (ESF) documenting the Investigator's assessment of each screened participant with regard to the protocol's inclusion and exclusion criteria is to be completed by the Investigator and kept at the investigational site.

Screening and pre-treatment assessments will be performed within 35 days prior to Day 1 unless otherwise specified.

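### Section 5.4 sets no maximum age for virology and tuberculosis results carried over at re-screening, so a late re-screen may have no hepatitis B or C result in the window that exclusion 29 names

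*Combined protocol and SAP*

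**What the plan says.** Section 5.4 (Screen Failures) allows re-screening and lists what must be redone. For the infection tests it says "Serologies for hepatitis B, HIV, and PCR for HCV need not be repeated, and screening for latent tuberculosis infection need not be repeated", provided they were done before. The other items in the list carry their own requirements: the endoscopy must fall in the 3 weeks before first dose, women of childbearing potential repeat the pregnancy test, and "Screening laboratory evaluation beyond those itemized above must be completed within 35 days of the starting dose".

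The related rules are these:

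- Section 5.2, exclusion 29, bars participants with HBsAg, with total HBcAb, or with a "positive hepatitis C by PCR test result at screening or within the 3 months prior to starting study treatment".
- Section 5.2, exclusion 28 ("Positive HIV antibody test") and exclusion 13 ("History of tuberculosis or a positive Quantiferon® Gold test") name no time window.
- Section 8.10.1 gives the general rule: "Screening and pre-treatment assessments will be performed within 35 days prior to Day 1 unless otherwise specified".
- Appendix 1, Section 1.3, requires a new consent form when re-screening comes more than 30 days after the last signature. It sets no latest date for re-screening. Section 5.1, criterion 1, allows consent up to 3 months before randomization, and a new signature restarts that period.
- Table 1 of the Schedule of Activities marks serology, viral PCR and the tuberculosis test at screening only.

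**The concern.** Within one list, the infection tests are the only carried-over laboratory results without a time limit. A participant who returns months later gives fresh safety bloods and has a fresh endoscopy, but may enter on old virology and tuberculosis results. No later scheduled visit would pick up an infection acquired in between.

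The protocol itself treats these infections as disqualifying, and it gives reasons to care about them. Section 2.3 states "There is a theoretical risk of immunosuppression from increased" regulatory T cells and names opportunistic infection among the theoretical risks. It adds that giving the drug on top of corticosteroids could raise infection risk further. Section 6.5.1 lets participants stay on steroids, thiopurines or methotrexate.

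The first stake is participant safety. The second is interpretation: safety is the primary objective, cohorts have about 8 participants on active drug, and an infection present before dosing but not detected could be recorded as a treatment-emergent event or liver abnormality.

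**Working it through.** The plan gives no figure of its own to reproduce. The check is whether any rule caps the age of the carried-over result and, if none does, how old it can be at first dose.

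**Is there a cap elsewhere?** The 35-day rule in Section 8.10.1 gives way where another section provides differently, and Section 5.4 does so. The consent rules fix when a new signature is needed, not when re-screening must end. Exclusions 13 and 28 have no window. Exclusion 29 has one, but Section 5.4 does not refer to it. No cap was found.

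**Age of the old result at first dose.** Let

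- W = wash-out or exclusion period in days (Section 5.2);
- x = days from the excluding exposure or episode to the first infection test (not in the documents; assumed 0 or more);
- s = days from the start of re-screening to Day 1 (1 to 35).

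If the participant returns on the earliest permitted day, age A = W − x + s. A later return adds to A without limit. Three months is taken as 91 days; 90 or 92 gives the same picture.

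| Reason for first failure | W | A at x = 0, s = 1 to 35 | When A exceeds 91 |
|---|---|---|---|
| 12-week wash-out (exclusions 18, 20, 21) | 84 | 85 to 119 | s > 7 + x |
| Herpes zoster, 3 months (exclusion 12) | 91 | 92 to 126 | s > x |
| Faecal transplant, 6 months (exclusion 17) | 182 | 183 to 217 | x up to about 91 for any s; x up to 125 at s = 35 |

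- **12 weeks:** at x = 0 the window is passed once re-screening takes 8 days or more. With a full 35-day screening, 84 − x + 35 > 91 gives x up to 27.
- **Faecal transplant:** taking 6 months as 183 days moves the upper end to 218. Exclusion 17 reads "per rectum within the last 6 months" and does not say whether that is counted back from screening. If it is counted back from first dose, A = 182 − x, which exceeds 91 when x is below 91.
- **Five half-lives (exclusion 18):** this exceeds 91 days only if the half-life exceeds 91 / 5 = 18.2 days. The documents give no half-lives for prior biologics. An assumed range of 14 to 30 days gives W from 84 (the 12-week floor) to 150, and A from 85 to 185 at x = 0.

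**Routes that stay inside 3 months.** A re-screen within 30 days of the consent signature gives at most about 30 + 35 = 65 days, if the tests were drawn after consent. An intestinal pathogen (exclusion 7, 35 days) gives about 35 + 35 = 70 days on the same earliest-return basis.

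**The case against.** The best defence is that the sections can all be obeyed as written. Exclusion 29 looks back for positive results. It does not say that a negative expires after 3 months, or that a negative must exist inside that period. A site could also treat the first screening result as the one obtained at screening. So a reader who infers a literal contradiction between Section 5.4 and exclusion 29 goes too far. The same holds for a supposed breach of the 35-day rule, because Section 5.4 is an express exception to it.

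Three further inferences are tempting and unsupported:

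- **That the 3-month window governs HIV and tuberculosis.** It covers hepatitis B and C only.
- **That the wash-outs necessarily push re-screening past the window.** Twelve weeks is 84 days, shorter than 3 months, and wash-outs run from last exposure, not from the first test. Someone tested 10 weeks after a 12-week agent waits 2 weeks, unless five half-lives is longer.
- **That the stopping rules would be triggered.** Section 4.1.3 needs related events of the same type in 2 or more participants and exempts those the Investigator judges unrelated. The documents give no number of re-screens and no infection rate.

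There are also partial safeguards. The waiver is permissive, and Appendix 4 lets the Investigator order extra tests at any time. Exclusions 2, 3, 11 and 13 still apply on history and judgement, and liver tests are repeated within 35 days. These soften the gap but do not close it: none requires a current serology, PCR or tuberculosis result.

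**Conclusion.** The point holds as a gap that should be closed. Followed as written, Section 5.4 lets a late re-screen be dosed with no hepatitis B or C result from the new screening or from the 3 months before first dose, the period by which exclusion 29 judges those infections. For HIV and tuberculosis, the finding is limited to the absence of any stated maximum age.

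Its size can be given only as test age. If the first test coincided with the exposure and the participant returned as early as allowed, the result is about 183 to 218 days old after a faecal transplant, 92 to 126 after herpes zoster, and 85 to 119 after a 12-week wash-out. The age falls day for day as the first test moves later after exposure, so the window may not be passed at all. Nothing bounds it from above if the return is delayed. How many participants this touches cannot be estimated from the documents.

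One assumption is that the 3-month phrase in exclusion 29 applies to HBsAg and HBcAb as well as to the HCV PCR. If it applies to the PCR alone, hepatitis B joins HIV and tuberculosis as a missing age limit. Sample size and analysis methods are unaffected.

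**What to change.** Reconcile Section 5.4 with exclusion 29 by adding a maximum age to the waiver. HBsAg, HBcAb and HCV PCR results would be carried over only if obtained within the 3 months before first dose, and otherwise repeated with the re-screening bloods. The sponsor should also state a maximum age for carried-over HIV and tuberculosis results. The same 3 months would be consistent, but the documents do not dictate it.

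The change is about one sentence. After a 12-week wash-out, a hepatitis repeat would be needed only when s > 7 + x. Re-screens within 30 days of consent would not be affected. Late re-screens already give blood for the repeated safety laboratory tests, so the downside is a few additional blood tests.

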## **5.5 RECRUITMENT PROCEDURES**

Participants will be identified for potential recruitment using pre-screening enrollment logs, clinical database and Independent Ethics Committees (IEC)/Institutional Review Board (IRB) approved newspaper/radio/social-media advertisements prior to consenting to take place on this study.

## **6. TREATMENTS**

Study treatment is defined as any investigational treatment(s), marketed product(s), placebo, or medical device(s) intended to be administered to a study participant according to the study protocol.

The investigational medicinal product (IMP) required for completion of this study will be provided by the Sponsor. Study drug will be administered by the investigational staff (i.e., Investigator or study nurse) at the study center under supervision of the Investigator.

## 6.1 TREATMENTS ADMINISTERED

[Table 5](#) summarizes the treatments administered.

**Table 5 Summary of Treatments Administered**

Study Treatment Name:	RO7049665	Placebo
Dosage Formulation:	Solution for injection	Solution for injection
Unit Dose Strength:	5.0 mg/mL	N/A
Dose:	Starting dose 3.5 mg (dose level 1), 7.5 mg (dose level 2), and 15 mg (dose level 3)	N/A
Route of Administration:	SC injection	SC injection
Dosing Instructions:	RO7049665 must be prepared for dosing under appropriate aseptic conditions and should be used immediately. The solution for injection must be filtered prior to use	Placebo must be prepared for dosing under appropriate aseptic conditions and should be used immediately. The solution for injection must be filtered prior to use
Packaging and Labeling:	RO7049665 and Placebo will be provided in 2 mL colorless glass vials. Each vial will be labeled as required per country requirement.	
Storage Conditions	For RO7049665 and Placebo, if not used immediately, the total storage time of the dose solution prior to administration should not exceed 24 hours to limit the risk of microbial growth in case of accidental contamination. The recommended storage condition for the dose solution is 2°C to 8°C, but dose solutions may be stored at room temperature for up to a maximum of 4 hours	
Manufacturer	F. Hoffmann-La Roche, Ltd.	F. Hoffmann-La Roche, Ltd.

Guidelines for dosage modification and treatment interruption or discontinuation are provided in [Section 6.6](#) or [Section 7](#), respectively.

Please see the [RO7049665 Investigator's Brochure](#) and Pharmacy Manuals for more details.

## 6.2 PREPARATION/HANDLING/STORAGE/ACCOUNTABILITY

Study drug packaging will be overseen by the Roche clinical trial supplies department and bear a label with the identification required by local law, the protocol number, drug identification and dosage.

The packaging and labeling of the study medication will be in accordance with Roche standard and local regulations.

The investigational site will acknowledge receipt of IMPs and confirm the shipment condition and content. Any damaged shipments will be replaced.

Upon arrival of the IMPs at the site, site personnel will complete the following:

- Check the IMPs for damage.
- Verify proper identity, quantity, integrity of seals and temperature conditions.
- Report any deviations or product complaints to the Monitor upon discovery.

The qualified individual responsible for dispensing the study treatment will prepare the correct dose according to the randomization/treatment assignment schedule and Pharmacy Manual.

The Investigator or delegate must confirm appropriate temperature conditions have been maintained during transit for all study treatment received and any discrepancies are reported and resolved before use of the study treatment.

Only participants enrolled in the study may receive study treatment and only authorized site staff may supply or administer study treatment. All study treatments must be stored in a secure, environmentally controlled, and monitored (manual or automated) area in accordance with the labeled storage conditions with access limited to the Investigator and authorized site staff.

The Investigator, Institution, or the Head of the Medical Institution (where applicable) is responsible for study treatment accountability, reconciliation, and record maintenance (i.e., receipt, reconciliation and final disposition records).

IMPs will either be disposed of at the study site according to the study site's institutional standard operating procedure (SOP) or returned to the Sponsor with the appropriate documentation. The site's method of IMP destruction must be agreed upon by the Sponsor. Local or institutional regulations may require immediate destruction of used IMP for safety reasons. The site must obtain written authorization from the Sponsor before any IMP is destroyed, and IMP destruction must be documented on the appropriate form.

Further guidance and information for the final disposition of unused study treatment are provided in the Pharmacy Manual or other specified location.

